NON-INTERVENTIONAL (NI) STUDY PROTOCOL

MULTINATIONAL Retrospective Chart Review Study to Assess the Characteristics, Treatment Outcomes and Resource Use Among Adult Patients Hospitalised for Community-Acquired Pneumonia (CAP) or Complicated Skin and Soft Tissue Infections (cSTI) Treated with Zinforo® (ceftaroline fosamil) in a Usual Care Setting

This document contains confidential information belonging to Pfizer. Except as otherwise agreed to in writing, by accepting or reviewing this document, you agree to hold this information in confidence and not copy or disclose it to others (except where required by applicable law) or use it for unauthorized purposes. In the event of any actual or suspected breach of this obligation, Pfizer must be promptly notified.

Study Information

Title	Multinational Retrospective Chart Review Study to Assess the Characteristics, Treatment Outcomes and Resource Use Among Adult Patients Hospitalised for Community-Acquired Pneumonia (CAP) and Complicated Skin and Soft Tissue Infections (cSSTI) Treated With Zinforo® (ceftaroline fosamil) in a Usual Care Setting
Protocol number	C2661041
Protocol version identifier	2.0
Date of last version of protocol	19 July 2019
Active substance	Other cephalosporins (ATC Code: J01DI02)
Medicinal product	Ceftaroline fosamil (Zinforo)®
Research question and objectives	
Primary Objective:
 
To provide real world evidence (RWE) on the characteristics, clinical management, treatment outcomes and healthcare resource use of adult patients aged 18 years and older admitted to the hospital for CAP or cSSTI who received Zinforo® in usual care before 31-May-2019 in Europe and Latin America.

Authors	PPD Ph.D. PPD PPD MHA PPD

2. LIST OF ABBREVIATIONS

Abbreviation	Definition
ABSSSI	Acute Bacterial Skin and Skin Structure Infections
AE	Adverse event
CABP	Community-Acquired Bacterial Pneumonia
CAP	Community-Acquired Pneumonia
CRF	Case report form
cSSTI	Complicated Skin and Soft Tissue Infections
eCRF	Electronic Case Report Form
EDC	Electronic Data Collection
EMA	European Medicines Agency
GPP	Good Pharmacoepidemiology Practices
HIPAA	Health Insurance Portability and Accountability Act
ICF	Informed consent form
ICU	Intensive Care Unit
ICMJE	International Committee of Medical Journal Editors
IEC	Independent Ethics Committee
IRB	Institutional review board
ISPE	International Society for Pharmacoepidemiology
IV	Intravenous
MIC	Minimum Inhibitory Concentration
MDR	Multidrug Resistant
RWD	Real World Data
RWE	Real World Evidence

Abbreviation	Definition
RWESA	Real World Evidence Strategy and Analytics
SAP	Statistical Analysis Plan
SOFA	Sequential Organ Failure Assessment
US	United States
WBC	White Blood Cell

4. ABSTRACT

Title:	Multinational Retrospective Chart Review Study to Assess the Characteristics, Treatment Outcomes and Resource Use Among Adult Patients Hospitalised for Community-Acquired Pneumonia (CAP) or Complicated Skin and Soft Tissue Infections (cSSTI) Treated With Zinforo® (ceftaroline fosamil) in a Usual Care Setting Version 2.0; 19 July 2019
Rational and background:	
cSSTI represents a major clinical problem^{1,2,3} and is associated with considerable morbidity, mortality, resource use and healthcare costs.⁴⁻⁹ Current treatment options are compromised by resistance and tolerability issues. CAP is a common respiratory illness¹⁰⁻¹⁶ that is also associated with considerable morbidity, mortality,^{15,17,18} resource use and healthcare costs.^{11,14,18,19}
 
In patients with CAP and cSSTI (particularly those at risk of treatment failure), there is a need for an alternative treatment option that will improve empiric treatment success rates by providing activity against a range of suspected causative pathogens (including MRSA and S. pneumoniae) combined with a good tolerability profile.
 
Ceftaroline fosamil (Zinforo®) is a novel 5th generation cephalosporin with rapid bactericidal action against a broad range of common Gram positive and Gram negative pathogens. Zinforo® is approved in the EU in adults and children from the age of two (2) months for the treatment of complicated skin and soft tissue infections (cSSTI) and community-acquired pneumonia (CAP).
 
For the treatment of cSSTI and CAP, the recommended dose of Zinforo® is 600 mg administered every 12 hours by intravenous infusion over 60 minutes (standard dose). For the treatment of adult patients with cSSTI confirmed or suspected to be caused by S. aureus with a Minimum Inhibitory Concentration (MIC) = 2 mg/L or 4 mg/L to ceftaroline, the dose of Zinforo® is 600 mg administered every 8 hours by intravenous infusion over 120 minutes (high dose). The recommended treatment duration for cSSTI is 5 to 14 days and the recommended duration of treatment for CAP is 5 to 7 days.
 
Zinforo® is an effective treatment for patients hospitalised with CAP or cSSTI, including those at risk of treatment failure and/or with intolerance/contraindications to commonly-used antibiotics.^{20,29, 30-32, 33} At present, the real-world use and effectiveness of Zinforo® in treating patients hospitalized with CAP and cSTTI has not been evaluated in a usual care setting in Europe and Latin America.

Research question and objectives:	
Study Aim:
 
The overall study aim is to provide real world evidence (RWE) on the characteristics, clinical management, treatment outcomes and healthcare resource use of adult patients aged 18 years and older admitted to the hospital for CAP or cSSTI who received Zinforo® in a usual care setting in Europe and Latin America on or before 31-May-2019.
 
Specific Objectives:
 
 • To describe the characteristics of patients hospitalized for CAP or cSSTI who received Zinforo® in a usual care setting in Europe and Latin America on or before 31-May-2019; • To describe physicians' use of Zinforo® in the clinical management of patients hospitalized for CAP or cSSTI in relation to their use of other antibiotics (first-line vs. second-line/salvage, monotherapy vs. combination therapy, empiric vs. definitive therapy); • To estimate the proportion of patients hospitalized for CAP or cSSTI who responded to Zinforo® (clinical response defined as no further intravenous (IV) antibiotic, switch to an oral antibiotic, or IV antibiotic treatment streamlining/de-escalation prior to discharge from the hospital); • To estimate the proportion of patients hospitalized for CAP or cSSTI who had treatment modification of Zinforo® (defined as switch to another IV antibiotic due to an adverse reaction, drug-drug interaction, insufficient response or a microbiological diagnosis indicating that the pathogen is not susceptible to Zinforo®); • To describe the clinical outcomes (eg, hospital readmission, mortality) of patients hospitalized for CAP or cSSTI after starting Zinforo® stratified by clinical response; • To describe the healthcare resource use of patients hospitalized for CAP or cSSTI after starting Zinforo® stratified by clinical response.
Study design:	Multinational, multicenter observational retrospective cohort study
Population:	The target population is adult patients aged 18 years and older hospitalized for CAP or cSSTI who received intravenous (IV)

	
Zinforo® treatment in a usual care setting in Europe and Latin America on or before 31-May-2019.
 
Inclusion criteria:
 
 1. Age 18 years or older at admission date to the hospital. 2. Received four (4) or more consecutive IV doses of Zinforo® in usual care on or before 31-May-2019; and 3. Admitting diagnosis to the hospital was either CAP or cSSTI. 
Exclusion criteria:
 
 1. Patients who were participating in an interventional clinical trial during the same hospital admission in which Zinforo® was administered. 2. Patients whose hospital medical records are missing documentation of the diagnostic criteria for either cSSTI or CAP. 3. Patients whose hospital medical records are missing details of dosing with Zinforo.® 4. Patients whose hospital medical records are missing information on the success/failure of Zinforo® treatment and the reason why treatment was discontinued; and 5. Patients whose hospital medical records are missing discharge date and status information.
Variables	
The following data will be collected:
 
 • Site Information (country, type of site, hospital size, participating department); • Patient Demographics (sex, age, ethnic origin, height, weight, type of residence/co-habitation, smoking habits); • Medical History (diabetes, respiratory disease, cancer/malignancy, peripheral vascular disease, congestive heart failure, immunosuppressive therapy in the 3 months prior to hospitalization, hospitalization in the prior 3 months, other relevant conditions, multidrug resistance risk score at admission, quick sequential organ failure

	
assessment score at admission);
 
• Disease Characteristics for CAP (time from diagnosis to Zinforo initiation, diagnostic criteria met, imaging findings suggestive of bacterial pneumonia, signs of acute illness at diagnosis);• Disease characteristics for cSSTI (time from diagnosis to initiation of Zinforo diagnostic criteria met, cellulitis/fasciitis, abscess, post-traumatic wound, post-surgical wound, diabetic leg ulcer, peripheral vascular disease ulcer, lesion size, lower extremities affected, swelling/induration, skin necrosis, recurrent skin infection episode, nosocomial infection);• Hospitalization Information (duration of hospitalization, discharge destination, discharge status, ICU duration, ICU discharge date);• Microbiological Diagnosis (investigations or diagnostic tests performed, positive microbiological diagnosis obtained, microorganism name, bacteremia diagnosed);• Zinforo® Treatment (treatment duration, line of therapy, time from hospital admission to first dose, empiric vs. definitive therapy, monotherapy vs. combination therapy, daily dose, number of doses administered, treatment duration, clinical response, clinical response definition (Halm criteria, switch to oral antibiotic, other) time to clinical response (days), treatment streamlining/de-escalation, treatment modification, time to treatment modification (days), reason for treatment modification, ICU vs. general medical ward administration);• All Other Antibiotic Treatments during the index hospital admission (each monotherapy/combination antibiotic therapy name, line of therapy, route of administration, duration of treatment, number of doses administered, treatment response, time to treatment modification from initial dose (days), reason for treatment modification, ICU vs. general medical ward administration);• Clinical Outcomes and Healthcare Resource Use after first Zinforo® dose (number of days in the hospital, switch to another IV antibiotic, switch to an oral antibiotic, time to first oral antibiotic dose, admission to ICU, time in ICU,
--	---

	mechanical ventilation, surgery, reinfection or recurrence, acute renal failure, length of acute renal failure, blood pressure support, fluid resuscitation, vasopressors, septic shock, isolation required, parenteral nutrition, length of parenteral nutrition, home-based care after discharge, in-hospital mortality, 30-day mortality, 30-day readmission after discharge).
Data sources	Data will be retrospectively extracted from the hospital medical records of eligible patients. De-identified data will be collected following the Health Insurance Portability and Accountability Act (HIPAA)-compliant safe harbor approach. ³⁴
Study size	The target sample for recruitment is approximately 600 patients across all sites. The number of eligible CAP and cSSTI patients that each site will provide will vary depending on the historical usage of Zinforo® at that site up to 31-May-2019.
Data analyses	
The objective of this retrospective chart review study is descriptive in nature; therefore, no hypothesis testing will be performed. The results of the total study sample will be summarized using descriptive statistics. Data will be summarized by means, standard deviations (SD), medians, minimums and maximums for continuous variables; and by numbers and percentages for categorical variables. All summarized data will be presented in aggregate, and may be stratified by covariates of interest if a subgroup has a minimum sample size of 30 patients (5% of total study size).
 
Clinical outcomes and resource use following the initiation of Zinforo® treatment will be assessed according to patients' observed clinical response time (<72-hours, >72-hours, no response). The mean (SD) and median times to an outcome of interest (eg, length of stay in the hospital measured in days) will be calculated in each patient subgroup.

Milestones	
Completion of feasibility assessment: 15 September 2019.
 
Start of data collection: 01 December 2019.
 
End of data collection: 15 June 2020.
 
Final study report: 12 October 2020.

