8. RESEARCH QUESTION AND OBJECTIVES

Study Aim:

The overall study aim is to provide real world evidence (RWE) on the characteristics, clinical management, treatment outcomes and healthcare resource use of adult patients aged 18 years and older admitted to the hospital for CAP or cSSTI who received Zinforo[®] in a usual care setting in Europe and Latin America on or before 31-May-2019.

Specific Objectives:

- To describe the characteristics of patients hospitalized for CAP or cSSTI who received Zinforo® in a usual care setting in Europe and Latin America on or before 31-May-2019.
- To describe physicians' use of Zinforo® in the clinical management of patients hospitalized for CAP or cSSTI in relation to their use of other antibiotics (first-line vs. second-line/salvage, monotherapy vs. combination therapy, empiric vs. definitive therapy).
- To estimate the proportion of patients hospitalized for CAP or cSSTI who responded to Zinforo® (clinical response defined as no further intravenous (IV) antibiotic, switch to an oral antibiotic, or IV antibiotic treatment streamlining/de-escalation prior to discharge from the hospital).
- To estimate the proportion of patients hospitalized for CAP or cSSTI who had treatment modification of Zinforo® (defined as switch to another IV antibiotic due to an adverse reaction, drug-drug interaction, insufficient response, or a microbiological diagnosis indicating that the pathogen is not susceptible to Zinforo®).
- To describe the clinical outcomes (eg, hospital readmission, mortality) of patients hospitalized for CAP or cSSTI after starting Zinforo® stratified by clinical response.
- To describe the healthcare resource use of patients hospitalized for CAP or cSSTI after starting Zinforo® stratified by clinical response.

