2.1.4 STUDY OBJECTIVES

The overall study aim of this study is to provide real world evidence (RWE) on the characteristics, clinical management, treatment outcomes and healthcare resource use of adult patients aged 18 years and older admitted to the hospital for CAP or cSSTI who received Zinforo® in a usual care setting in Europe and Latin America on or before 31-May-2019.

Specific objectives of this study are to analyze for the CAP and cSSTI cohorts:

- Objective 1 “Patient characteristics”: To describe the characteristics of patients hospitalized for CAP or cSSTI who received Zinforo® in a usual care setting in Europe and Latin America on or before 31-May-2019
- Objective 2 “Use of Zinforo”: To describe physicians’ use of Zinforo® in the clinical management of patients hospitalized for CAP or cSSTI in relation to their use of other antibiotics (first-line vs. second-line/salvage, monotherapy vs. combination therapy, empiric vs. definitive therapy)
- Objective 3 “Clinical response”: To estimate the proportion of patients hospitalized for CAP or cSSTI who responded to Zinforo® (clinical response defined as no further intravenous (IV) antibiotic, switch to an oral antibiotic, or IV antibiotic treatment streamlining/de-escalation prior to discharge from the hospital);
- Objectives 4 “Additional clinical outcomes”: To describe the clinical outcomes (eg, hospital readmission, mortality) of patients hospitalized for CAP or cSSTI after starting Zinforo® stratified by clinical response;
- Objective 5 “Treatment modification”: To estimate the proportion of patients hospitalized for CAP or cSSTI who had treatment modification of Zinforo® (defined as switch to another IV antibiotic due to an adverse reaction, drug-drug interaction, insufficient response or a microbiological diagnosis indicating that the pathogen is not susceptible to Zinforo®)
- Objective 6 “Healthcare resource use”: To describe the healthcare resource use of patients hospitalized for CAP or cSSTI after starting Zinforo® stratified by clinical response.

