4.1.4 SUBGROUPS

For selected outcomes, subgroup analyses will be conducted by geography (Europe including Russia, Latin America).

Certain outcomes will be stratified by covariates of interest provided each of the strata exceeds the minimum sample size of 30 patients (5% of total) as specified in the protocol. Covariates for stratified analyses will include:

- For cSSTI patients: Early response within 3 days
- For CAP patients: Early response within 4 days
- Line of treatment
- Age: >65 or ≤65

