8.1.3 HEALTHCARE RESOURCE USE FOR PATIENTS WITH CAP STARTING ZINFORO

Table 8. Utilization during index hospitalization in patients with CAP

Resource utilization	All CAP patients (N=XX)
	n %
Duration of index hospitalization (days)	
Mean (SD)	
Median (Min-Max)	
Duration of days in ICU	
Mean (SD)	
Median (Min-Max)	
Quick sepsis-related organ failure assessment (qSOFA) conducted	
Yes	
No	
Unknown	
If qSOFA was conducted (n, % of qSOFA assessed)	
Glasgow coma scale <15	
Systolic blood pressure <100 mmHg	
High respiration rate (\geq 22 breaths per minute)	
Patient required isolation	
Yes	
No	
Unknown	
If patient isolated:	
Duration of isolation (days)	
Mean (SD)	
Median (Min-Max)	
Unknown	

Abbreviations: ICU: intensive care unit; Max: maximum; Min: minimum; qSOFA: Quick sepsis-related organ failure assessment; SD: standard deviation.

Table 9. Hospitalisation cost in patients with CAP

Hospital Cost	All CAP patients (N=XX)	
	n	%
Hospital Cost - standard hospital (local currency)		
Mean (SD)		
Median (Min-Max)		
Hospital Cost - advanced level (local currency)		
Mean (SD)		
Median (Min-Max)		
Hospital Cost - standard hospital (USD)		
Mean (SD)		
Median (Min-Max)		
Hospital Cost - advanced level (USD)		
Mean (SD)		
Median (Min-Max)		

Abbreviations: USD: US Dollars, Max: maximum; Min: minimum; SD: standard deviation.

Table 10. Utilization during index hospitalization by response status in patients with CAP

Resource utilization	CAP responders (N=XX)		CAP non- responders (N=XX)	
	n	%	n	%
Duration of index hospitalization (days)				
Mean (SD)				
Median (Min-Max)				
Duration of days in ICU				
Mean (SD)				
Median (Min-Max)				
Quick sepsis-related organ failure assessment (qSOFA) conducted				
Yes				
No				
Unknown				
If qSOFA was conducted (n, % of qSOFA assessed)				
Glasgow coma scale <15				
Systolic blood pressure <100 mmHg				
High respiration rate (\geq 22 breaths per minute)				
Patient required isolation				
Yes				
No				
Unknown				
If patient isolated:				
Duration of isolation (days)				
Mean (SD)				
Median (Min-Max)				
Unknown				

PFIZER CONFIDENTIAL

CCI

Table 11. Hospitalisation cost by response status in patients with CAP

Hospital Cost	CAP responders (N=XX)		CAP non- responders (N=XX)	
	n	%	n	%
Hospital Cost- standard hospital (local currency)				
Mean (SD)				
Median (Min-Max)				
Hospital Cost- advanced level (local currency)				
Mean (SD)				
Median (Min-Max)				
Hospital Cost- standard hospital (USD)				

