8.1.10 HEALTHCARE RESOURCE USE FOR CSSTI PATIENTS STARTING ZINFORO

Table 35. Utilization during index hospitalization in patients with cSSTI

Resource utilization	All cSSTI patients (N=XX)	
	n	%
Duration of index hospitalization (days)		
Mean (SD)		
Median (Min-Max)		
Duration of days in ICU		
Mean (SD)		
Median (Min-Max)		
Quick sepsis-related organ failure assessment (qSOFA) conducted		
Yes		
No		
Unknown		
If qSOFA was conducted		
(n, % of qSOFA assessed)		
Glasgow coma scale <15		
Systolic blood pressure <100 mmHg		
High respiration rate (\geq 22 breaths per minute)		
Patient required isolation		
Yes		
No		
Unknown		
If patient isolated:		
Duration of isolation (days)		
Mean (SD)		
Median (Min-Max)		
Unknown		

Abbreviations: ICU: intensive care unit; Max: maximum; Min: minimum; qSOFA: Quick sepsis-related organ failure assessment; SD: standard deviation.

Table 36. Hospitalisation cost in patients with cSSTI

Hospital Cost	All cSSTI patients (N=XX)	
	n	%
Hospital Cost - standard hospital (local currency)		
Mean (SD)		
Median (Min-Max)		
Hospital Cost - advanced level (local currency)		
Mean (SD)		
Median (Min-Max)		
Hospital Cost - standard hospital (USD)		
Mean (SD)		
Median (Min-Max)		
Hospital Cost - advanced level (USD)		
Mean (SD)		
Median (Min-Max)		

Abbreviations: USD: US Dollars, Max: maximum; Min: minimum; SD: standard deviation.

Table 37. Utilization during index hospitalization by response status in patients with cSSTI

Resource utilization	cSSTI responders (N=XX)		cSSTI non- responders (N=XX)	
	n	%	n	%
Duration of index hospitalization (days)				
Mean (SD)				
Median (Min-Max)				
Duration of days in ICU				
Mean (SD)				
Median (Min-Max)				
Quick sepsis-related organ failure assessment (qSOFA) conducted				
Yes				
No				
Unknown				
If qSOFA was conducted (n, % of qSOFA assessed)				
Glasgow coma scale <15				
Systolic blood pressure <100 mmHg				
High respiration rate (\geq 22 breaths per minute)				
Patient required isolation				
Yes				
No				
Unknown				
If patient isolated:				
Duration of isolation (days)				
Mean (SD)				
Median (Min-Max)				
Unknown				

PFIZER CONFIDENTIAL

CCI

Table 38. Hospitalisation cost by response status in patients with cSSTI

Hospital Cost	cSSTI responders (N=XX)		cSSTI non- responders (N=XX)	
	n	%	n	%
Hospital Cost- standard hospital (local currency)				
Mean (SD)				
Median (Min-Max)				
Hospital Cost- advanced level (local currency)				
Mean (SD)				

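### Stay and bed-day cost are tabulated by a response status reached during the same stay, so by-response differences carry a built-in artefact of unknown, possibly material size

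*Protocol*

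**What the plan says.** **Protocol.** The Data analyses entry in section 4 groups patients by "observed clinical response time (<72-hours, >72-hours, no response" and reports the mean, SD and median of outcomes such as "length of stay in the hospital measured in days" in each group. Section 8 counts as response the end of IV antibiotics, a switch to oral therapy, or "IV antibiotic treatment streamlining/de-escalation prior to discharge from the hospital".

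**SAP.** Objective 6 in section 2.1.4 is "To describe the healthcare resource use of patients hospitalized for CAP or cSSTI after starting Zinforo® stratified by clinical response". Section 4.1.4 moves the time cut: "For cSSTI patients: Early response within 3 days" and "For CAP patients: Early response within 4 days". The tables that carry stay and cost, however, have two columns and no time cut. Table 10 is "Utilization during index hospitalization by response status in patients with CAP" and Table 37 is "Utilization during index hospitalization by response status in patients with cSSTI"; Tables 11 and 38 do the same for cost (numbering as in the body of the SAP).

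Three further SAP provisions matter:
- Section 5.1.2 takes response from a yes/no CRF item and lists death, from the index infection or from another cause, among the clinical failures. Tables 22 and 49 set response against failure.
- Section 5.1.8 records stay as the whole index admission and computes cost as bed days times a per diem rate.
- No landmark or comparable method is planned, and neither the SAP nor protocol section 9.9 (Limitations) mentions the issue.

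**The concern.** The grouping variable is not known at the start of the period being counted. It is settled during that period, and the way it is settled depends on how long the patient stays.

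Two separate mechanisms follow. In the three-level split, a patient can be a late responder only by being alive and under observation past the cut, which is guarantee time. In the two-column tables there is no cut, but a death ends the stay and also places the patient among the failures. Either mechanism can produce a difference in mean stay when response and stay are unrelated, and the cost formula passes it on in proportion.

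A second problem adds to this. Objective 6 concerns resource use after Zinforo is started, and protocol section 9.3 lists hospital days after the first dose. The SAP's stay includes the days before it, which the response to Zinforo cannot have affected.

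At stake is a reader taking adjacent responder and non-responder columns as the days and money that response saves or costs.

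**Working it through.** **1. Figures in the documents.** There is no expected stay, response time or effect size to reproduce. The related arithmetic agrees: 5% × 600 = 30 patients as minimum stratum; 550/647 = 85.0% and 316/398 = 79.4% success in the US chart review cited in protocol section 7, implying 15% to 21% non-response. Section 9.9 of the protocol equates four doses with at least two days at twice-daily dosing. The extra time guaranteed to a late responder is therefore about 3 − 2 = 1 day at a 3-day cut and 4 − 2 = 2 days at a 4-day cut.

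**2. Late versus early responders.** Null simulation with stay L (from first dose) independent of latent response time T, so any gap is artefact. Assumptions, none from the documents: L = 2 days plus a lognormal, mean 7, 10 or 14 days, SD 50% or 80% of the mean; T lognormal, median 2.5, 3 or 4 days, log-SD 0.5. Two treatments of a patient discharged before T were tried.

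| Late minus early, mean days | 3-day cut | 4-day cut |
|---|---|---|
| Discharge before T is non-response | 0.1 to 2.2 | 0.3 to 3.0 |
| Discharge counts as response, 18% unrelated failures | 0.0 to 1.2 | 0.0 to 2.3 |

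The gap is smallest for long stays and largest for a 7-day mean with wide spread. Example (mean 10, SD 8, median T 3, 3-day cut): 10.0 versus 11.2 days in the first row, 9.9 versus 10.1 in the second.

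**3. Responders versus non-responders, with deaths as failures.** Assume mean stay m, in-hospital death probability d with death uniform between day 2 and the stay the patient would otherwise have had, and other failures f, all independent. A death loses on average (m − 2)/2 days, and deaths make up d/(d + f − df) of the failures:

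gap = (m − 2)/2 × d/(d + f − df)

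- m = 7, d = 0.05, f = 0.10: 2.5 × 0.05/0.145 = 0.9 days
- m = 10, d = 0.05, f = 0.10: 4 × 0.05/0.145 = 1.4 days
- m = 10, d = 0.15, f = 0.05: 4 × 0.15/0.1925 = 3.1 days
- m = 14, d = 0.15, f = 0.05: 6 × 0.15/0.1925 = 4.7 days

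Over d = 5% to 15% and f = 5% to 10%, non-responders look 0.9 to 4.7 days shorter, with d + f − df (non-response) between 10% and 24%, a range that covers the 15% to 21% above. Simulation gives the same values. Without deaths, and with failures unrelated to stay, the gap is about 0.

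**4. Landmark.** Take patients still in hospital at day 3 or 4, classify them by response so far, and count the remaining stay. The difference between early responders and those not yet responding is then 0.0 days (within 0.04) in every scenario of step 2. Later events cannot move a patient between groups. The landmark keeps 91% to 100% of patients at day 3 and 71% to 100% at day 4. Under a gamma stay with mean 10 and SD 6 days, 7% have left by day 3 and 13% by day 4.

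**The case against.** The study is descriptive and runs no tests. A mean stay among responders is a correct description of those patients, and neither document proposes a causal reading. That stands: the tables are not wrong in themselves, and there is no type I error to protect. It does not make the columns safe to compare, and a stated limitation is the least that is needed.

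A reader might infer that the artefact alone produces a more than twofold gap. A model can be built that way: with a gamma stay (mean 10, SD 6), median response time 4 days (log-SD 0.6), and everyone discharged before responding labelled a non-responder, mean stay is 11.3 versus 4.7 days, a ratio of 2.4. The documents do not support that labelling. Under protocol section 8, leaving off IV therapy is itself a response, and discharge before response is not on the SAP's failure list. With 18% failures unrelated to stay and discharge counted as response, both groups average 10.0 days.

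It is also fair that the guaranteed-stay argument belongs to the three-level split and does not carry over to the two-column tables; there the argument rests on deaths. Nor is the direction settled: failure followed by another IV drug may lengthen the stay, and that was not simulated.

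Finally, a landmark changes the question. It merges late responders with those who never respond and drops early discharges, so it cannot replace the display that Objective 6 asks for. That also stands, which is why it is proposed only as an addition.

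**Conclusion.** The concern holds as a matter of structure: both forms of the by-response comparison condition on something decided during the stay being counted, and neither document handles or mentions it. The magnitude is not established. The ranges above rest on assumed distributions, on independence of stay and response, and, for the death mechanism, on reading the SAP's non-responders as its clinical failures. The table shells do not spell this out.

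What can be said is that the artefact runs from negligible to several days, and that real prolonged illness may offset or reverse it. The documents do not support saying that the tables will show a large spurious gap, or that non-responders will necessarily look cheaper. The changes are worth making because they are cheap and remove an ambiguity that the raw columns cannot resolve.

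**What to change.** 1. Keep Tables 10, 11, 37 and 38, but count stay and bed-day cost from the first Zinforo dose. The time from admission to first dose is already collected (SAP section 5.1.7).
2. Within each response group, show in-hospital deaths separately from patients discharged alive, and state how the non-responder column is formed.
3. Add a landmark display at the SAP's early-response cut (day 3 cSSTI, day 4 CAP): patients alive and in hospital at that day, grouped by response up to it, with remaining stay, cost and mortality counted from it. Include ICU days only if ICU dates are available; the SAP lists ICU use as a duration.
4. State the limitation in the SAP and the report.
5. Reconcile the protocol's 72-hour cut with the SAP's 3- and 4-day cuts; as the protocol is worded, a response at exactly 72 hours falls in neither group.

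**Cost.** SAP wording and modest programming, largely on data already collected. Patients discharged or dead before the landmark leave that display (up to 9% at day 3 and 29% at day 4 over the ranges assumed above) and should be counted beside it. Patients with unknown time to response drop out too, since the SAP does not impute.
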